Study Protocol and Statistical Analysis Plan

Title of Study: Effects of Transcutaneous Vagus Nerve Stimulation (taVNS) in Individuals with Primary Dysmenorrhea: A Randomized Controlled Study

NCT Number: NCT06146569

Date of Document: September 18, 2023

Table of contents

	Page number
Study Protocol	3
Objectives	3
Design	3
Methods	3
Statistical Analysis Plan	4

Study Protocol

Objectives:

This study aims to investigate the effects of transcutaneous auricular vagus nerve stimulation (taVNS) on pain, functional and emotional symptoms, and physical performance in individuals with primary dysmenorrhea (PD).

Design:

A small randomized controlled trial design was conducted online at two time points: 1) baseline/pre-test and 2) post-test (one week after pre-test). Data were collected by face-to-face interview method.

Participants will be randomly assigned to one of two conditions: 1) intervention (women received taVNS treatment) or 2) sham (Sham applications were applied using a current-free headset specifically designed for this purpose. Participants observed the device's functionality but supplied no current).

The study was approved by the Artvin Çoruh University Rectorate Scientific Publications Ethics Committee (date: 18/09/2023, procedure number: E-105136) and was by the ethical standards of the World Medical Association (Declaration of Helsinki).

Methods:

Sample and Recruitment. Women who had never given birth before participated in the study. To participate in the research, the following criteria must be met: 1) being diagnosed with PD according to the No. 345 Primary Dysmenorrhea Consensus Guidelines; 2) an NRS score of at least three during menstruation before treatment; 3) being a woman between the ages of 18-40; 4) a regular menstrual cycle of 28 ± 7 days; 5) being nulliparous; 6) no history of brain surgery, tumor, or intracranial metal implantation; 7) No chronic genitourinary infection or alcohol or drug use. Potential participants were invited to study at Artvin Çoruh University through voice announcements and brochures. Following diagnosis with primary dysmenorrhea at Artvin State Hospital, those who met the study's inclusion criteria received treatment at Artvin Çoruh University Physiotherapy Laboratory between November 2023 and January 2024.

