Procedure. The current of taVNS was applied bilaterally from the tragus and turbinate parts of the ear with the VagustimTM device. The current frequency used in modulation mode is 10 Hz, and the pulse width was 300 μ s (In modulation mode, the pulse rate and width are automatically changed in a loop pattern. The pulse width was reduced by 50% from its original setting in 0.5 seconds; then, the pulse rate was changed in 0.5 seconds, reduced by 50% from the original setting. Total cycle time is 1 second.). The current intensity was applied for 5 minutes, keeping the current constant where the participant felt comfortable. Sham applications were applied using a current-free headset specifically designed for this purpose. Participants observed the device's functionality but supplied no current.

Measures.

Numerical Rating Scale (NRS). Data was queried separately for lower abdominal, waist, and bilateral thigh pain. Participants were required to complete an NRS questionnaire through the Google Forms web survey platform (Google LLC, Mountain View, CA, USA) before bed at

night on days 1, 2, and 3 of two consecutive menstrual cycles. The questionnaire was based on the most severe pain they experienced during the day. The minimum score of the NRS is 0, and the maximum score is 10. Higher scores are associated with more severe pain intensity.

Pressure Pain Threshold (PPT). Fabrication Enterprises, Inc., used a Push-Pull Force Gauge® (1200-304) to measure the pressure pain threshold. This handheld algometer allows linear force application ranging between 0 and 10 kg (22 lb × ¼ lb and 10 kg × 100 g). Initially, two exercises were performed on the dominant forearm's extensor muscles to familiarize patients with the equipment. The evaluator positioned the algometer perpendicular to each point and applied gradual pressure at a constant rate of approximately 0.5 kg/cm²/s. The pressure was increased until the participant reported feeling pain. Each point was evaluated three times, and the average value was recorded. The measurement was performed on five reference points in the abdomen and one reference point in the lumbar spine, as in a previous study where pain was evaluated in PD.

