IBM SPSS version 28.0 software (IBM Corp., Armonk, NY, USA) was utilised for statistical analysis. Before the statistical analysis, the Shapiro-Wilk normality test was used to assess data distribution because of $n < 50$. Demographic data and clinical baseline variables were compared among the 2 groups by independent samples t-test for continuous variables and a χ^2 test for categorical variables. Continuous variables were expressed as mean \pm standard deviation (SD), while categorical variables were reported as number and frequency. The independent and paired samples t-test was compared to normally distributed variables between two groups. Two-way analysis of variance (ANOVA) was used for multiple comparisons of normally distributed

variables. The effects of stimulation on pain, pressure pain threshold, menstrual symptoms, and physical performance were calculated using a mixed ANOVA, where the dependent variables were pain, pressure pain threshold, menstrual symptom, and physical performance score, and the independent fixed variables were time, stimulation group (taVNS and sham), and interaction term was group vs time. Post hoc comparisons were carried out when appropriate using Bonferroni correction for multiple comparisons. Greenhouse-Geisser correction was applied when the assumption of sphericity was violated. In the F tests, partial eta squared (η^2) was used as an effect size indicator, elucidated as small, 0.01; medium, 0.06; and large, 0.14. In the t-tests, Cohen's d (d) was used as an effect size indicator, elucidated as small, 0.2; medium, 0.5; large, 0.8. A p value of <0.05 was considered statistically significant.

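### NRS pain is tested by group × time with no baseline covariate and an open time factor; on the two-level reading, ANCOVA on the first-cycle mean usually gains precision at little cost, provided that cycle precedes stimulation

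*Combined protocol and SAP*

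**What the plan says.** The Statistical Analysis Plan lists pain among the dependent variables of a mixed ANOVA and states that "the independent fixed variables were time, stimulation group (taVNS and sham), and interaction term was group vs time". No covariate is named. Baseline enters elsewhere only as a comparison: "Demographic data and clinical baseline variables were compared among the 2 groups by independent samples t-test".

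The NRS paragraph under Methods, Measures has ratings made at night on "days 1, 2, and 3 of two consecutive menstrual cycles", and adds: "Data was queried separately for lower abdominal, waist, and bilateral thigh pain". That is 3 × 2 = 6 ratings per site.

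The Design section gives two time points: "1) baseline/pre-test and 2) post-test (one week after pre-test". Sample and Recruitment requires "a regular menstrual cycle of 28 ± 7 days" and, as an entry rule, "an NRS score of at least three during menstruation before treatment". Neither section says in which cycle, or on which day, stimulation was given. The entry rule is not tied to either of the two recorded NRS cycles.

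**The concern.** Pain is the first outcome named in the Objectives, and the sample is below 50. Two matters are left open.

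First, the time factor for NRS could be two cycle means, six nights, or a cycle-by-night layout. The two time points in the Design section suggest two levels. The SAP's Greenhouse-Geisser sentence points the other way, because sphericity is an issue only with more than two levels, and NRS is the one outcome whose stated schedule has more than two occasions. The sentence may be standard wording, so the layout cannot be settled from the text. Left open, it is a choice that could be made after the data are seen.

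Second, on the two-level reading the first-cycle rating enters with a fixed weight. In a small trial, a better weight for data already collected can be worth several points of power.

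**Working it through.** **Inputs.** From the documents: two randomised arms, three nights in each of two cycles, significance at 0.05, n below 50. Assumed, because the documents do not give them: 1:1 allocation, a two-sided test, N of 24 to 48, the correlation r between first- and second-cycle means, the ratio k of second- to first-cycle SD, and the effect size. The plan states no power or sample-size figure, so there is none to reproduce.

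**Step 1: what the planned test is.** With two time levels, the group × time F statistic is the square of the two-sample t statistic on change scores. In a cycle-by-night layout the group × cycle term is the same test.

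**Step 2: variances.** In units of the first-cycle variance:
- change score: 1 + k² − 2rk
- ANCOVA: k²(1 − r²)
- difference, change minus ANCOVA: (1 − rk)², which is never negative

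The residual variance under ANCOVA is therefore never larger, and the two are equal only when the slope rk is 1. The price is estimating that slope: an expected factor of (N−3)/(N−4), which is 21/20 = 1.050 at N=24, 37/36 = 1.028 at N=40 and 45/44 = 1.023 at N=48, plus one degree of freedom. With k=1 the variance ratio is (1 + r)/2.

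**Step 3: power at N=40.** The shift is set so that the change score has 80% power (noncentral F on 1 and N−2 degrees of freedom). For example, at r=0.5 and k=1 the change-score variance is 1, its standard error √(4/40) = 0.316, and the required shift 0.909 SD. The ANCOVA variance is 0.75 × 37/36 = 0.771, its standard error 0.278, and 0.909/0.278 = 3.27 gives about 89% power.

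| r | Ratio, k=1 | ANCOVA power, k=1 | Ratio, k=1.2 | ANCOVA power, k=1.2 |
|---|---|---|---|---|
| 0.38 | 0.69 | 91% | 0.81 | 87% |
| 0.5 | 0.75 | 89% | 0.87 | 84% |
| 0.7 | 0.85 | 85% | 0.97 | 80% |
| 0.8 | 0.90 | 83% | 1.00 | 79% |
| 0.88 | 0.94 | 81% | 0.99 | 79% |

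With k=1 and r from 0.38 to 0.88, the range is 91-80% at N=24, 91-81% at N=30 and 92-82% at N=48. With k=0.7 the gain is larger: the squared confidence-interval width falls to 0.41-0.53 of the change-score value over r of 0.3 to 0.9 and N of 20 to 48.

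**Step 4: worst case.** At slope 1 (r=0.8, k=1.25), simulated power for change score and ANCOVA is 79.8% and 77.8% at N=24, 80.2% and 79.2% at N=40, and 80.1% and 79.2% at N=48.

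**Step 5: bounded scale and entry rule.** Simulations with integer scores ("The minimum score of the NRS is 0, and the maximum score is 10") and entry at 3 or more, over 20 scenarios at N=40, gave 78-81% for the change score and 79-91% for ANCOVA.

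**Step 6: chance imbalance.** At N=40 the baseline t-test reaches significance at 2.024 × √(4/40) = 0.64 SD. A chance first-cycle difference of 0.5 SD is below that. With k=1 it shifts the change-score estimate by (1 − r) × 0.5, which is 0.31 SD at r=0.38 and 0.06 SD at r=0.88; ANCOVA removes the shift. Averaged over randomisations, both tests keep a type I error of 5%.

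**Step 7: if six levels were meant (N=40).** For an effect equal on all nights, sized for 80% change-score power, the six-level interaction has 56-79%. For uneven effects, with correlations of 0.7 within and 0.5 between cycles:

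| Effect on nights 1, 2, 3 (SD) | ANCOVA | Six-level |
|---|---|---|
| 1, 0.8, 0.6 | 94% | 90% |
| 1, 0.6, 0.2 | 74% | 87% |
| 0.8, 0.8, 0 | 64% | 88% |
| 1, 0, 0 | 30% | 92% |

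**The case against.** The strongest reply is that this is a preference. The planned test is valid under randomisation, and a reader who infers from the missing covariate that the plan ignores baseline would be wrong: a change score uses baseline, with slope 1. That stands, and the point claims only efficiency.

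The size of the gain is also unproven. The documents give no SD or correlation, and a second-cycle SD only 1.2 times the first removes the advantage at r of 0.7 or more. That stands too. It reduces the expected gain but leaves the loss small.

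Nor can two levels be taken as intended. The Greenhouse-Geisser sentence leaves six levels open, and if the effect sits on the first night or two, a cycle mean gives up real power. This is a reason to choose in advance and to keep nightly results.

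Finally, nothing confirms that the first NRS cycle is pre-treatment. One might infer from the entry rule that it is, but that rule only requires some menstrual NRS score before treatment. Without confirmation the ANCOVA should not be adopted. The planned test would then lack a true baseline as well, so the objection does not favour leaving the plan as written.

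**Conclusion.** The point holds as a cheap improvement, with medium confidence. On the two-level or group × cycle reading, ANCOVA gains up to about 11 points of power at N=40 when r is low and the cycle SDs are equal. The gain shrinks to about 1 point at r=0.88, and to nothing or a loss of about 1 point when the second-cycle SD is 1.2 times the first and r is 0.7 to 0.88. The largest loss is about 1 point at N=40-48 and 2 at N=24. All of this rests on assumed N, r and SDs, and on a first cycle free of stimulation.

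A reader might infer that the planned analysis is biased or has an inflated error rate, or that the trial will lose some 10 points of power. The documents support neither: the test is valid, and the gain depends on quantities they do not give.

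**What to change.** 1. Reconcile the Design section's one-week interval with the NRS schedule. Under the 28 ± 7 day criterion, consecutive cycles begin 21 to 35 days apart. State where stimulation falls relative to the two NRS cycles.
2. If the first cycle wholly precedes stimulation, name the mean of nights 1-3 in each cycle as the NRS summary for each site. Test the group difference in the second-cycle mean by ANCOVA with the first-cycle mean as covariate, in place of group × time.
3. If it does not, do not use the first-cycle mean as a covariate.
4. Keep nightly results, including a group × night term, as secondary. If nights are missed, a mixed model with baseline means constrained equal across groups can use all available ratings.

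The cost is SAP wording and one timing statement; no new data are needed. The downsides are about 1-2 points of power if the slope is near 1, and less power than a six-level test if the effect is concentrated on the first night or two. There is one test per site, so which site leads, and multiplicity across sites, remain to be settled separately.

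### Effects are expressed only as partial eta squared and Cohen's d with fixed labels, with no between-arm difference in scale units and no confidence interval, in a trial small enough for chance alone to reach the medium cut-off fairly often.

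*Combined protocol and SAP*

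**What the plan says.** The Statistical Analysis Plan section names two effect measures. For F tests it uses partial eta squared, "elucidated as small, 0.01; medium, 0.06; and large, 0.14". For t-tests it uses Cohen's d, "elucidated as small, 0.2; medium, 0.5; large, 0.8". Continuous data are summarised by mean and SD, and the significance rule is "A p value of <0.05 was considered statistically significant". The main model is a mixed ANOVA in which "the independent fixed variables were time, stimulation group (taVNS and sham), and interaction term was group vs time".

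Nothing restricts the verbal labels to significant effects. The section names no between-arm difference in scale units as the reported effect. It names no confidence interval for a mean difference, for eta squared or for d.

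The only information on size is the reason given for the normality test: "the Shapiro-Wilk normality test was used to assess data distribution because of $n < 50". There is no planned N, allocation ratio or power statement, and the text does not say whether n is the total or per group.

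**The concern.** Partial eta squared is a proportion of variation, so its sample value is zero or above even when there is no effect, and the smaller the trial, the further above zero it tends to lie. A fixed label attached to that point estimate can therefore describe noise as an effect of some size.

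Without an interval, a reader of a small trial cannot readily separate a result that argues against a worthwhile effect from one that is merely uninformative. A value of eta squared also does not say how many NRS points, kilograms of pressure or metres walked separate the arms, which is what a clinician needs.

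**Working it through.** The plan states no error rate or power, so there is no figure of its own to reproduce. The check asks how often the labels would be reached when there is no true effect.

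**Inputs from the documents**
- Cut-offs: 0.01, 0.06 and 0.14 for partial eta squared; 0.2, 0.5 and 0.8 for d (Statistical Analysis Plan).
- Two arms: "Participants will be randomly assigned to one of two conditions" (Design).
- Two time points: "two time points: 1) baseline/pre-test and 2) post-test (one week after pre-test" (Design). The group-by-time interaction then has 1 and N−2 degrees of freedom.
- Alpha 0.05 (Statistical Analysis Plan).

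**Assumptions**
- Total N of 49, 40, 30 or 20, because the documents give only an upper bound.
- Equal arms for the calculations on d.

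**Partial eta squared under no effect.** For one numerator degree of freedom, eta² = F / (F + N − 2). Hence P(eta² ≥ c) = P(F(1, N−2) ≥ c(N−2)/(1−c)). At N=40 and c=0.06, F = 0.06 × 38 / 0.94 = 2.43, for which p = 0.128. The null distribution is Beta(0.5, (N−2)/2), with mean 1/(N−1). The smallest significant value is F_crit/(F_crit + N − 2).

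| Assumed total N | Null mean | P(≥0.01) | F at 0.06 | P(≥0.06) | P(≥0.14) | Smallest value with p<0.05 |
|---|---|---|---|---|---|---|
| 49 | 0.021 | 49% | 3.00 | 9.0% | 0.8% | 0.079 |
| 40 | 0.026 | 54% | 2.43 | 12.8% | 1.7% | 0.097 |
| 30 | 0.034 | 60% | 1.79 | 19.2% | 4.2% | 0.130 |
| 20 | 0.053 | 67% | 1.15 | 29.8% | 10.4% | 0.197 |

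A simulation of 200,000 null two-arm, two-time-point designs at each of N=40, 30 and 20 gave 12.6%, 19.2% and 29.7% for the 0.06 cut-off, in agreement.

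The medium cut-off lies below the significance threshold at every N in the table. At N=40 the gap runs from 0.06 to 0.097. At N=20 even the large cut-off of 0.14 lies below the threshold of 0.197.

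**Cohen's d under no effect.** With equal arms, P(|d| ≥ 0.5) = P(|t(N−2)| ≥ 0.5√(N/4)). At N=40 this is P(|t(38)| ≥ 1.58) = 12.2%. At N=49, 30 and 20 it is 8.7%, 18.2% and 27.8%. For an unadjusted two-group comparison at N=40, an observed d of 0.5 has a 95% interval of about −0.13 to 1.13.

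**Sensitivity**
- If n below 50 is per group, a total of 98 gives 1.5% for the 0.06 cut-off.
- NRS pain is collected at "night on days 1, 2, and 3 of two consecutive menstrual cycles" (Measures), so the pain model may have more than two time levels. Under sphericity, three levels give 9.5% at N=40 and 17.7% at N=30; six levels give 3.7% and 11.9%. These are below the one-degree-of-freedom rates. At N=20 the order reverses slightly: 32.8% and 34.1% against 29.8%.

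**The case against.** The strongest reply is that the plan keeps p<0.05 as its criterion for significance and presents eta squared and d only as indicators. It nowhere says that a non-significant result will be described as a small or medium effect. A null effect that is both significant and at least medium occurs at most 5% of the time. This stands: the rates above are the chance that the cut-off is reached, and the plan does not commit to wording a report that way. But it does not exclude it either, since the labels attach to the F tests and t-tests in general.

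The second reply is that means and SDs are planned, so the data will appear in scale units and a reader with the group sizes could build an interval for the post-test difference. This stands in part. For the difference in change, the reader also needs the pre-post correlation, or must work back from a reported F. The information is recoverable with effort, but it is not presented.

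The third reply is that no rate can be fixed from these documents. This stands. A reader might infer that n below 50 implies a rate of about one in eight; that needs a total N near 40 and one numerator degree of freedom, and neither is assured. A reader might also multiply a rate by a count of outcomes. The count depends on whether pain sites, pressure points and scales are counted singly, and the mixed ANOVA sentence names only four outcome domains. The documents do not support a single expected number of chance labels.

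**Conclusion.** The point holds as a reporting weakness. Effects are expressed only through point estimates with fixed labels, without a scale-unit difference and without an interval, and one of the two measures is biased upward at this size. If n below 50 is the total and the effect has one degree of freedom, chance alone reaches the medium cut-off in about 9% of tests at N=49, and more at any smaller N: 13% at 40, 19% at 30 and 30% at 20. If the bound is per group, the rate can be as low as 1.5%.

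Two stronger readings are not supported. The plan does not state that non-significant outcomes will be called medium. The interval quoted for d is for an unadjusted two-group comparison and not for the planned group-by-time effect, whose precision in scale units depends on a pre-post correlation that the documents do not give. The validity of the tests is not in question, so this is a low-severity, low-cost improvement.

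**What to change.** For each outcome, make the main reported effect the between-arm difference in change, or the baseline-adjusted difference, in the outcome's own units (NRS points, kg, metres, questionnaire points) with its 95% confidence interval. State the total and per-arm N beside it.

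If a standardised measure is kept, give it with an interval, and use omega squared in place of partial eta squared. Replacing d by Hedges' g matters little: at N=40 the correction factor is 1 − 3/(4 × 38 − 1) = 0.98.

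Delete the small/medium/large rule. Keeping the labels only where the interval excludes zero is not a good substitute, because it acts as a significance filter. At N=40 only |d| of about 0.64 or more would be labelled, and the effects so selected would tend to be overstated.

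The cost is a few sentences in the SAP and somewhat more table work, with no new data. Reported standardised effects become smaller. For example, at N=40 an eta squared of 0.06 (F = 2.43) corresponds to an omega squared of about (F − 1)/(F − 1 + N) = 1.43/41.43 = 0.034, treating the interaction as a two-group comparison of change scores.

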Menstrual Symptom Questionnaire (MSQ). The scale consists of 22 items and uses a 5-point Likert-type format. Participants were asked to rate the severity of their menstrual symptoms on a scale of 1 (never) to 5 (always). The scale contains three subscales: 'Negative Effects/Somatic Complaints' (items 1-13), 'Menstrual Pain Symptoms' (items 14-19), and 'Coping Methods' (items 20-22). The maximum score on the scale is 110, and the minimum score is 22. MSQ score is calculated by taking the average score of all items in the scale. High scores are associated with increased menstrual symptoms.

Functional and Emotional Measure of Dysmenorrhea (FEMD). Scale consisting of 14 items, evaluates dysmenorrhea functionally and emotionally with a 5-point Likert-type item. The reliability and validity study of the scale developed in 2012. As the scores obtained from the scale with a minimum score of 14 and a maximum score of 70 increase, the functional and emotional impact of dysmenorrhea also increases.

Hamilton Anxiety Scale (HAM-A). Patients with chronic pain often experience mood disorders, such as depression and anxiety. The Hamilton Anxiety Scale (HAM-A) was used to assess the intensity of anxiety symptoms. The scale measures both mental and physical anxiety with 14 symptom-defined items. Each item is scored from 0 (not present) to 4 (severe). The total score range is 0-56. On the anxiety scale, scores of 17 or below indicate mild anxiety, while scores of 18-24 indicate moderate anxiety, and scores of 25-30 indicate severe anxiety.

6-Minute Walk Test (6MWT). The 6-Minute Walk Test (6MWT) was evaluated submaximal functional capacity. 6MWT measures the maximum distance participants can walk as quickly as possible for six minutes.

Positive and Negative Affect Schedule (PANAS). For taVNS administration, the positive and negative affect was assessed before and after treatment using the Positive and Negative Affect Schedule (PANAS). This 5-point Likert-type scale was developed in 1988 and includes 20 items: 10 positive and ten negative. A score range of 10-50 assesses both positive and negative effects.

Statistical Analysis Plan

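### No primary outcome is named among seven instruments, and nothing in the plan controls error across outcomes

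*Combined protocol and SAP*

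**What the plan says.** - **Objectives.** The aim is to study the effects of taVNS "on pain, functional and emotional symptoms, and physical performance in individuals with primary dysmenorrhea (PD"). The areas stand side by side with no order of importance.
- **Methods, Measures.** Seven instruments are described. None is called primary or secondary. PANAS is introduced with the words "For taVNS administration, the positive and negative affect was assessed before and after treatment", which leaves open whether it is to be compared between groups as an efficacy outcome.
- **Statistical Analysis Plan, model.** For the mixed ANOVA, "the dependent variables were pain, pressure pain threshold, menstrual symptom, and physical performance score". That is four domains. HAM-A and PANAS are not named, nor is FEMD, unless it is meant to fall under menstrual symptoms.
- **Statistical Analysis Plan, error control.** "Post hoc comparisons were carried out when appropriate using Bonferroni correction for multiple comparisons". This follows the ANOVA description and comes just before "Greenhouse-Geisser correction was applied when the assumption of sphericity was violated". The section ends with "A p value of <0.05 was considered statistically significant".
- **Timing.** Design places the second assessment at "post-test (one week after pre-test"). The NRS entry under Measures collects scores at "night on days 1, 2, and 3 of two consecutive menstrual cycles".

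**The concern.** A significance threshold controls error only for the tests to which it is tied. Here a single 0.05 applies to every test, the set of tests is not fixed, and no test is singled out to answer the objective. With several outcomes each tested at 0.05, the chance that at least one favours taVNS by luck rises well above the chance for one test, and the plan puts no limit on which outcome is then presented as the finding. The document contains no sample size calculation from which a primary outcome could be inferred. At stake is whether a significant result from this randomised sham comparison can be read as evidence of efficacy.

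**Working it through.** The plan states no family-wise error rate, power or sample size, so there is no figure of its own to reproduce. The calculation below measures what its rule allows.

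**Inputs from the documents**

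- Threshold 0.05 per test (Statistical Analysis Plan).
- Two arms, so one between-group contrast per outcome (Design).
- Four domains named for the mixed ANOVA (Statistical Analysis Plan).
- Seven instruments (Measures). PANAS gives two scores and each other instrument is counted once: 6 + 2 = 8 scores, or 6 without PANAS.

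**Assumptions**

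- Tests are two-sided (the plan does not say), so a false result in favour of taVNS has probability 0.05/2 = 0.025 per test.
- There is one test per outcome and no true effect on any outcome.
- All pairs of outcomes share one correlation ρ. No correlations are given, so 0, 0.5 and 0.7 are shown.

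**Formulas for k tests**

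- Independent: benefit 1 − 0.975^k; either direction 1 − 0.95^k.
- Correlated, benefit: 1 − ∫ φ(u) Φ((1.96 − √ρ·u)/√(1−ρ))^k du. For either direction, replace the Φ term by the probability that a statistic lies between −1.96 and 1.96 given u.

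Worked at ρ = 0:

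- k = 4: 1 − 0.975^4 = 0.096 and 1 − 0.95^4 = 0.185.
- k = 8: 1 − 0.975^8 = 0.183 and 1 − 0.95^8 = 0.337.

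| Tests | Benefit, ρ = 0 / 0.5 / 0.7 | Either direction, ρ = 0 / 0.5 / 0.7 |
|---|---|---|
| 1 | 2.5% | 5% |
| 4 (domains named for the ANOVA) | 9.6 / 7.8 / 6.5% | 18.5 / 15.6 / 13.0% |
| 6 (PANAS left out) | 14.1 / 10.4 / 8.2% | 26.5 / 20.7 / 16.4% |
| 8 (all scores) | 18.3 / 12.5 / 9.5% | 33.7 / 25.0 / 19.1% |

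**Small-sample check.** Two-sample t-tests were simulated with an assumed 24 per arm, ρ = 0.7 and 60,000 trials. False benefit was 6.7% for four outcomes and 9.7% for eight, in line with the table.

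**Higher correlation.** At ρ = 0.8 the chance of a false benefit is 5.7% (four) and 7.9% (eight). At ρ = 0.9 it is 4.7% and 6.0%.

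**Limits.** The counts leave out the separate NRS sites and nights, the six PPT points and the MSQ subscales; nothing is claimed about tests within an instrument. If a model has more than two within-subject levels, as the Greenhouse-Geisser sentence allows, an interaction F test has no single direction and the benefit column is approximate.

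**The remedy under the same assumptions.** With one primary and seven secondaries (1,000,000 draws), Holm applied only after a significant primary gives any false benefit in 2.6 / 2.5 / 2.5% at ρ = 0 / 0.5 / 0.7. Without that gate the figures are 3.3–4.9%.

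**The case against.** The best defence is that this is a small investigative study. The aim is worded as investigation, the design is described as small, no confirmatory claim is made, and effect sizes are planned alongside p values. Whether such a study needs family-wise control is arguable. That stands as a reason to accept an exploratory label. It does not rescue the present text, which never calls the results exploratory and does apply a significance rule.

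Second, the percentages depend on choices the documents do not make. Independence is hard to credit for outcomes that share pain content and come from the same women, so the upper ends are extremes. The eight-score count is a scenario: only the four domains are tied to a named model. Both points stand, and the figures should be read as illustrations. The direction survives, since at ρ = 0.9 four tests still give 4.7%, nearly twice 2.5%.

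Third, Bonferroni is already in the plan. It is, but for post hoc comparisons, in the sentences on the ANOVA, and nothing extends it across outcomes.

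Fourth, much of the document is in the past tense, so outcomes may already have been analysed. A primary outcome named after that would be chosen with knowledge of the data. This stands, and it is why the exploratory route has equal place in the remedy.

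**Conclusion.** The concern holds. That no primary outcome and no error rule across outcomes are stated is plain from the text, and confidence in that is high. The size is illustrative: a false benefit in 6.5–9.6% of null trials with four tests, 8.2–14.1% with six and 9.5–18.3% with eight, against 2.5% for one primary test. These figures rest on two-sided testing, one test per outcome, and a common correlation from 0.7 down to 0. The trial remains usable, but as written its p<0.05 rule cannot support an efficacy claim. This should be fixed; the point does not invalidate the study.

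**What to change.** There are two acceptable routes, and the choice is the sponsor's.

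**Route A, only if outcomes have not yet been analysed:**

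1. Reconcile the one-week post-test in Design with the two-cycle NRS collection in Measures, so that a time point can be defined. With cycles of 28 ± 7 days the shortest is 21 days, so two cycles do not fit in one week.
2. Name one primary outcome, its time point and its between-group comparison, at two-sided 0.05. The planned group-by-time test may be kept.
3. List the secondary outcomes and test them by Holm at 0.05 only if the primary is significant.
4. Report subscales, single nights and single measurement points descriptively unless they are listed.

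**Route B, at the sponsor's choice, and the only route if outcomes have been analysed:** label all results exploratory and make no claim of efficacy from p<0.05.

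**Cost.** Both routes change wording only and need no extra participants or data. Route B costs the efficacy claim. Under Route A there is no formal secondary claim if the primary fails, and secondary thresholds tighten. With seven secondaries Holm's first step is 0.05/7 = 0.0071; with nine (the three NRS sites listed separately) it is 0.05/9 = 0.0056.

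The SAP gives only n < 50. If that is the total and the arms are equal, 24 per arm is the largest case. The standardised difference detectable with 80% power by a two-sample t-test (noncentral t) is then:

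| Per arm (assumed) | At 0.05 | At 0.0071 |
|---|---|---|
| 24 | 0.83 | 1.06 |
| 20 | 0.91 | 1.17 |
| 12 | 1.20 | 1.57 |

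At 0.0056 with 24 per arm it is 1.09. For a group-by-time test with two time points, these differences are in units of the change-score SD.
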